
B.1. SPECIFIC AIMS

This proposal will investigate the impact of whole plant cannabis on pain, affect, and inflammation among RA patients ($n = 66$). We will administer two cannabis formulations via vaporization (placebo and medium THC [3.6%]/medium CBD [5.4%]) across two experimental sessions using a counter-balanced, double-blind, crossover design. THC doses in the medium potency range will be tested in combination with CBD in the

medium potency range. With respect to inflammation outcomes, prior studies have demonstrated efficacy of cannabis with a 1:1 ratio of THC:CBD. Therefore, we hypothesize that cannabis in the medium THC potency range in combination with medium potency CBD will decrease inflammatory biomarkers relative to placebo.

Aim 1. To determine whether cannabis acutely reduces pain and negative affect as compared to placebo.

- a. We hypothesize that, relative to placebo, cannabis (medium THC/medium CBD) will decrease subjective reports of pain.
- b. We hypothesize that, relative to placebo, cannabis (medium THC/medium CBD) will decrease subjective reports of negative affect.
- c. We hypothesize that blood THC and CBD levels will be negatively correlated with subjective reports of pain and negative affect.

Aim 2. To determine whether cannabis acutely reduces markers of inflammation (IL-1 α , IL-1 β , IL-6 and TNF- α) as compared to placebo.

- a. We hypothesize that, relative to placebo, cannabis (medium THC/medium CBD) will decrease blood markers of inflammation.
- b. We hypothesize that inflammation marker levels will be positively correlated with subjective reports of pain and negative affect, and negatively correlated with blood THC and CBD levels.

B.2. SAMPLE DESCRIPTION AND RECRUITMENT

Human subject involvement is necessary to complete this research proposal ($n = 66$). This proposal will require patients with rheumatoid arthritis (RA) or psoriatic arthritis (PA) to participate in laboratory cannabis administration sessions. Patients will be initially screened by phone or at the clinic, followed by a rigorous medical and diagnostic screening at intake. We describe recruitment procedures, inclusion criteria for participation, rationale for the proposed population, and retention strategies below.

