Statistical Analysis Plan: The sample size required for the proposed study is based on the primary outcome: pain assessment score. Using the results on SF-MPQ pain at present from Blake and colleagues to inform our parameters, we assume that participants will have a reduction in pain of 0.72 points following active cannabis compared to placebo cannabis with a standard deviation of the mean difference of 2.0715. We calculate the necessary sample size using a 2-period, 2-treatment, crossover design, comparing cannabis to placebo. At a two-sided significance level of 0.05, a design encompassing 66 patients will have power equal to 0.79 to detect this difference with this standard deviation.

The primary aim of this investigation is to assess current self-reported pain level (SF-MPQ) following cannabis administration (THC versus placebo). A one-sided t-test will be conducted to compare pain level following vaporization of each dose.

References

1. Nahin RL. Estimates of Pain Prevalence and Severity in Adults: United States, 2012. *J Pain Off J Am Pain Soc.* 2015 Aug;16(8):769–780. PMID: PMC4562413

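### The sample size assumes a two-sided 0.05 test, but the primary analysis is a one-sided t-test with no stated level, so the rule for a positive result is not fixed

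*Combined protocol and SAP*

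**What the plan says.** The plan for the primary outcome is two short paragraphs under Statistical Analysis Plan in section B.4.

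- **Sizing paragraph.** It assumes a difference of 0.72 points on SF-MPQ present pain, "with a standard deviation of the mean difference of 2.0715", in a two-period, two-treatment crossover. It then states: "At a two-sided significance level of 0.05, a design encompassing 66 patients will have power equal to 0.79".
- **Analysis paragraph.** It names current SF-MPQ pain as the primary aim and gives the test: "A one-sided t-test will be conducted to compare pain level following vaporization of each dose". It states no level.

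Section B.1, Aim 1a, gives the hypothesis a direction: "relative to placebo, cannabis (medium THC/medium CBD) will decrease subjective reports of pain". No other section states a level for the primary test.

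**The concern.** The two paragraphs describe different tests unless the one-sided test is run at 0.025, which the plan does not say. The only level in the document is 0.05, and it is attached to a two-sided test. A reader could carry 0.05 over to the one-sided test, or could use 0.025 so that the analysis matches the sizing.

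The choice matters because the two readings can give opposite conclusions from the same data. At one-sided 0.05, a favourable result with a two-sided p-value between 0.05 and 0.10 would count as positive; at one-sided 0.025 it would not. If the level is still open when the data are unblinded, it could be chosen with the result in view.

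A one-sided test is not wrong in itself, since Aim 1a is directional. The faults are the missing level and the conflict with the sizing.

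**Working it through.** **Inputs, all from the sizing paragraph**

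- Difference d = 0.72 points.
- SD of within-patient differences: printed as 2.0715. This may be 2.07 followed by reference number 15, which is an assumption, so both values were run.
- n = 66, each patient receiving both treatments.
- Level: two-sided 0.05.

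The calculation treats the comparison as within-patient, with 65 degrees of freedom (paired t) or 64 (two-period crossover). The analysis sentence does not say that the t-test is paired; the sizing paragraph's crossover design implies it.

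**Step 1. Reproduce the stated power.**

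SE = SD/√n = 2.07/√66 = 0.2548.

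Noncentrality = d/SE = 0.72/0.2548 = 2.826.

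Power is the probability that a noncentral t with this parameter exceeds the critical value. For two-sided 0.05 with 65 df the critical t is 1.997, and power is 0.795. Across both SDs and both degrees of freedom, power is 0.794 to 0.795. The stated 0.79 is reproduced.

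**Step 2. Repeat for the one-sided readings** (SD 2.07, 65 df).

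| Test | Critical t | Smallest significant difference (critical t × SE) | Power at 0.72 | False benefit claim if no effect |
|---|---|---|---|---|
| Two-sided 0.05 | 1.997 | 0.509 | 0.795 | 2.5% |
| One-sided 0.025 | 1.997 | 0.509 | 0.795 | 2.5% |
| One-sided 0.05 | 1.669 | 0.425 | 0.875 | 5.0% |

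One-sided 0.05 gives 0.875, not 0.79, so the sizing did use two-sided 0.05. At one-sided 0.05, about 52 patients would have been enough for power 0.79. A simulation of 200,000 trials with no effect gave false benefit rates of 0.0500 at one-sided 0.05 and 0.0249 at one-sided 0.025.

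**Step 3. Find where the readings disagree.**

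If the observed SD equals 2.07, they disagree for observed differences from about 0.43 to 0.51 points. Take an observed difference of 0.47:

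- t = 0.47/0.2548 = 1.845
- one-sided p = 0.035; two-sided p = 0.070
- 95% CI = 0.47 ± 1.997 × 0.2548 = −0.04 to 0.98

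This result is positive at one-sided 0.05 and negative at two-sided 0.05 or one-sided 0.025.

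**Step 4. Chance that the trial lands in the disputed range** (t between 1.669 and 1.997).

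| True difference | Probability |
|---|---|
| 0 | 2.5% |
| 0.36 (half the planned effect; an assumption, not in the plan) | about 12% |
| 0.72 | 0.875 − 0.795 = 8.0% |

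**The case against.** The strongest reply is that the plan never says the test will be run at one-sided 0.05. If 0.025 is meant, nothing is inflated and the defect is an omitted number. This is correct, and it is why the 5% figure is conditional. It does not remove the problem, because a reader cannot tell which level is meant and the document has no other text to settle it.

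It can also be said that a one-sided and a two-sided test at 0.05 have the same total type I error, 5%. That is true. The one-sided test puts all of it in the direction of benefit, while the two-sided test puts half there. The doubling therefore concerns false claims of benefit only, which is the error that matters for Aim 1a.

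The practical effect is moderate: the disputed range is narrow, the sample size is unaffected, and power is not reduced on either reading. That limits the size of the problem, but the problem still sits in the success rule for the primary outcome.

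Finally, fixing the level does not complete the primary analysis. The analysis paragraph does not say that the test is paired and names no primary time point, although pain is assessed several times after vaporization. Section B.2 calls for baseline VAS pain as a covariate in all analyses, which a plain t-test cannot include. These points stand, but they are separate and the change below does not settle them.

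**Conclusion.** The concern holds. The power of 0.79 belongs to a two-sided 0.05 test (equivalently one-sided 0.025 for benefit), while the planned test is one-sided with no level. If it is run at 0.05, the false-benefit rate is 5% instead of 2.5%, and the threshold for success falls from about 0.51 to 0.43 points. If it is run at 0.025, only the statement of the level is missing.

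The figures rest on a within-patient analysis of all 66 patients, normally distributed differences and, for the thresholds, an observed SD equal to the planned one. Reading the SD as 2.07 or 2.0715 makes no material difference. The inconsistency itself depends on none of these assumptions. Because it leaves the primary decision rule open, it should be corrected before unblinding.

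**What to change.** In the analysis paragraph, replace the one-sided test with a two-sided t-test at the 0.05 level, reported with a two-sided 95% confidence interval. Stating one-sided 0.025 would be equivalent for the benefit claim. Under either wording, 66 patients and power 0.79 stand unchanged.

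If one-sided 0.05 is really intended because Aim 1a is directional, justify it before unblinding, state that level in both paragraphs, and restate the power as about 0.875.

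The cost is one sentence and no additional patients. Compared with one-sided 0.05, the recommended wording sets a stricter criterion (about 0.51 rather than 0.43 points, power 0.795 rather than 0.875), which is the criterion the trial was sized for.

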Compensation/Reimbursement: Participants will be compensated \$50 for the baseline session, \$100 for each of two cannabis administration sessions, and will receive an additional \$50 bonus for completion of all experimental sessions for a maximum total of \$300. Ineligible subjects will be paid \$10 and excluded from participation. Due to experimental sessions involving cannabis administration, participants will be transported home following each experimental session via taxi, Uber, or other rideshare service.

B.4. METHODOLOGY

Synopsis. This study will be the first to investigate the effect of vaporized CB on pain, affect, and markers of inflammation among patients with RA. This research will be conducted over two Aims. Aim 1: To determine whether CB acutely reduces RA-associated pain and negative affect as compared to placebo. Aim 2: To determine whether CB acutely reduces markers of inflammation (IL-1 α , IL-1 β , IL-6 and TNF- α) as compared to placebo. Using a randomized, placebo-controlled, crossover design, participants ($n = 66$) will vaporize CB (placebo and medium THC/medium CBD) over two experimental sessions. Blood will be collected during each session (pre-vaporization, 10 min post-vaporization, 60 min post vaporization). Self-reported pain and affect will be assessed at the same time points.

Baseline Session: Following online/phone screening, potential subjects will meet remotely with research staff for a videocall to complete the study consent forms and discuss any questions. Participants will then attend an in-person baseline screening session at the laboratory to confirm eligibility and complete a physical exam. They will be asked to refrain from alcohol for 24 hours and caffeine for 2 hours prior to experimental sessions. Subjects will complete an alcohol breathanalysis for breath alcohol concentration (BrAC), and urine drug screen and pregnancy test (females). Subjects with a positive BrAC will be rescheduled. Tobacco smokers will be permitted to smoke a cigarette following the CO test to prevent nicotine withdrawal. Subjects will be administered a medical screening questionnaire to rule out history of adverse reaction to CB, and the MINI to make diagnostic exclusions of suicidality and key DSM-5 diagnoses (psychosis, panic disorder).

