Experimental CB Administration Sessions (1-2): Information including medications and pain level will be reconfirmed the morning of experimental sessions to maintain study eligibility. At each experimental session, BrAC and carbon monoxide (CO) level will be tested to confirm no recent alcohol or CB use. CO level must be 8ppm or below in order to proceed with the session; levels that are higher than 8ppm may be given some time to decrease to 8ppm (i.e. we will re-test) at the PI's discretion. Cigarette smokers will be given an opportunity for a smoking break after the test if they would like. Subjects will complete urine toxicology screening to confirm no other drug use. Females will be tested for pregnancy at each session. Vital signs will be obtained. Subjects will consume a calorie-controlled breakfast and complete pre-administration measures and questionnaires, an automatically inflating blood pressure (BP) cuff will be secured to continuously record heart rate and BP during the entire experimental session, and blood collection procedures will be implemented (see Figure 1). Participants will complete physical function testing^{20,21}. Participants will then vaporize the assigned CB dose and complete post-administration subjective measures of pain, affect, and drug effects. CB vaporization procedures will begin at 11am in order to reduce variability in pain that may occur throughout the day. Subjects will vaporize CB using a Storz & Bickel MIGHTY Vaporizer apparatus. Approximately 250mg CB will be ground to maximize surface area and will be placed in the vaporizer. The vaporizer will be prepared exclusively by study staff or the PI. Using the step-by-step quick-start guide and manual, study staff will prepare the vaporizer and will give it to the participant. The vaporizer device will be used on a dry surface away from paper and other flammable substances. A cued-puff procedure²² will standardize CB administration. Participants will listen to an audio-recording that will signal them to “get ready” (5 seconds), “inhale” (5 seconds), “hold vapor in lungs” (10 seconds), “exhale,” and to wait before repeating the inhalation cycle (40 seconds). A research assistant and the study nurse will continuously monitor the subject during the vaporization session via two-way mirror. In our previous studies which employed the paced-puffing procedure for combustible CB cigarettes with similar THC levels, all participants were able to complete an entire cigarette in 9 puffs in 8 mins on average^{18,19}. All participants will be required to complete 9 inhalations according to standardized procedures. Following cannabis administration (peak effects at 20-min post vaporization), participants will complete assessments including pain and affect. Peak THC/CBD levels will be assessed. Pain and affect will continue to be assessed three times over the recovery period at 1-hour intervals.

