
Figure 1. Schedule of Activities for Experimental Sessions.

Blood Sampling Procedures: We will collect blood at 3 time-points during each experimental session for analysis of inflammatory biomarkers (i.e., IL-1 α , IL-1 β , IL-6, IL-10, IL-17A, TNF- α , INF γ , MCP1, BDNF; sCD14); whole blood for future genetic analysis, if the participant consents to that portion; cannabinoid plasma levels (i.e., THC and CBD) pre-CB administration, at the termination of the CB administration procedure (10 mins post-completion of CB administration), and 60 mins post-completion of CB administration. These time-points were selected to characterize the impact of acute CB administration on pain and affect immediately following administration and at a delayed time-point (60-minutes post completion) to assess the duration of analgesia. Individual blood draws will be conducted in an antecubital vein at each pre-designated time point (see Figure 1). Blood samples will be collected in heparinized tubes (0.15 μ l heparin) and placed on ice immediately after each blood draw. Within 15 minutes of collection, blood will be centrifuged and plasma will

be transferred to a microtube and stored at -30°C. Plasma will be analyzed for inflammatory biomarkers and cannabinoid levels using gas chromatography/mass spectrometry (GC-MS) techniques.

Blood samples taken at the baseline/physical exam will be analyzed: i.e. IL-1 α , IL-1 β , IL-6, IL-10, IL-17A, TNF- α , INF γ , MCP1, BDNF; sCD14; CRP; cannabinoid plasma levels (i.e., THC and CBD); creatinine, AST, ALT; whole blood for future genetic analysis (if the participant consents to that portion, as it is optional)

Blood samples taken at the experimental sessions will be analyzed: i.e. THC, CBD, IL-1 α , IL-1 β , IL-6 and TNF- α , sCD14, CRP

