Sobriety Assessment: Subjects will remain in the laboratory for 3-hours following CB vaporization (psychotropic effects taper off within 2-3 hours²⁴), during which time snacks and water will be provided. Vital signs will be monitored and resumption of normal vital signs will be required for discharge. Subjects will then be evaluated for motor signs of intoxication. To ensure there are no residual cannabis effects 3 hours post-vaporization, participants will complete and pass a field sobriety test (i.e., heel-to-toe walking test, single leg raise balance test)²⁵. Following successful completion of the field sobriety test, subjects will be transported home via train, taxi, rideshare, or with a responsible adult to avoid driving following CB use. In the event of a failed test, participants will remain in the laboratory 20 more minutes until repeat testing is completed and passed.

Discharge Criteria: Participants will be permitted to leave the laboratory three hours following vaporization and only following a 75% reduction in their peak heart rate level during the experimental session. Blood pressure will be required to return to baseline ranges (below 160/100 and above 90/60). To ensure there are no residual cannabis effects 3 hours post vaporization, participants will complete and pass a field sobriety test (i.e., heel-to-toe walking test, single leg raise balance test). In the event of a failed test, participants will remain in the laboratory 20 more minutes until repeat testing is completed and passed.

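### Does the primary t-test on SF-MPQ pain need a change because the plan does not say which post-dose score it uses?

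*Combined protocol and SAP*

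**What the plan says.** The Statistical Analysis Plan paragraph (end of section B.4) takes current pain on the SF-MPQ as the primary outcome and compares it between active and placebo cannabis: "A one-sided t-test will be conducted to compare pain level following vaporization of each dose". For sample size it says "we assume that participants will have a reduction in pain of 0.72 points following active cannabis compared to placebo cannabis", with an SD of 2.07 (printed as 2.0715, where the last two digits are probably citation 15), 66 patients, two-sided 0.05 and power 0.79. Neither statement gives a time after dosing.

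Other places bear on timing:

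- **B.1, Aim 1:** "To determine whether cannabis acutely reduces pain and negative affect as compared to placebo".
- **B.4, Synopsis:** blood is drawn before vaporization and at 10 and 60 minutes after it, and "Self-reported pain and affect will be assessed at the same time points".
- **B.4, Experimental CB Administration Sessions:** "Following cannabis administration (peak effects at 20-min post vaporization), participants will complete assessments including pain and affect"; then "Pain and affect will continue to be assessed three times over the recovery period at 1-hour intervals".
- **B.4, Blood Sampling Procedures:** the draw times are justified as showing the effect "on pain and affect immediately following administration and at a delayed time-point (60-minutes post completion) to assess the duration of analgesia".
- **B.4, Sobriety Assessment:** patients stay three hours because "psychotropic effects taper off within 2-3 hours".

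Figure 1, the schedule of activities for the experimental sessions, is not shown in the text available.

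**The concern.** A t-test in a two-period crossover needs one number per patient per session. The Synopsis supplies two post-dose pain scores. The session procedures supply a score after dosing and three more, so about four. The two descriptions do not match on their face, and neither marks a score as primary.

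The times may not be equivalent. The plan separates an immediate effect from the duration of analgesia and puts peak effects at 20 minutes. A test at 10 minutes and one at three hours could therefore answer different questions, and the 0.72-point assumption is tied to neither. Two things would be at stake. The false-positive rate would rise if the most favourable time were chosen once the data were seen. Power would fall if the tested score carried less than the assumed effect.

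**Working it through.** **1. The plan's own figure.** Inputs from the Statistical Analysis Plan: n = 66, difference 0.72, SD of the within-patient difference 2.07, two-sided 0.05.

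- Standard error = 2.07/√66 = 0.2548.
- Noncentrality = 0.72/0.2548 = 2.826, with 65 degrees of freedom.
- Two-sided critical value 1.997; power by noncentral t = 0.795. With SD 2.0715 it is 0.794.

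The stated 0.79 reproduces. The calculation uses one score per session, as the single t-test does.

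**2. The schedules side by side.**

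| Source in B.4 | Post-dose pain scores |
|---|---|
| Synopsis | 10 and 60 min |
| Experimental sessions | one after dosing (peak effects put at 20 min), then three at 1-hour intervals |
| Blood Sampling Procedures | blood at 10 and 60 min; pain appears only as the reason for these times |

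The hourly scores depend on where counting starts:

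- From the end of vaporization: 60, 120, 180 min.
- From a first score at 10 min: 70, 130, 190 min.
- From a first score at 20 min: 80, 140, 200 min.

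The first reading contains the Synopsis's 60-minute score, so the two descriptions can be made to agree (an early score, then 60, 120 and 180). The other readings give no 60-minute score. They cannot be ruled out for running past 180 minutes, because three hours is the earliest discharge and B.3 describes 5-hour sessions.

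**3. What a data-driven choice would cost.** Take k one-sided tests under the null with equal correlation r between times, and claim success if any is significant. The rate is 1 − P(all k statistics fall below the critical value), from the multivariate normal. The plan states no level for its one-sided test, so 0.05 is an assumption, as is r.

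| k | r = 0.9 | r = 0.8 | r = 0.5 |
|---|---|---|---|
| 2 | 6.8% | 7.5% | 8.8% |
| 4 | 8.8% | 10.6% | 14.4% |

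At one-sided 0.025 the range from r = 0.9 to 0.5 is 3.5–4.5% (k = 2) and 4.7–7.8% (k = 4). With one score fixed in advance, k = 1 and the rate is the nominal level, whichever time is used.

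**4. What a weaker effect at the tested time would cost.** Same test (one-sided 0.05, critical value 1.669, 65 degrees of freedom). The retained fractions are assumed, since the documents give no time course for pain.

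| Effect retained | Difference | Noncentrality | Power |
|---|---|---|---|
| 100% | 0.72 | 2.826 | 0.875 |
| 75% | 0.54 | 2.119 | 0.674 |
| 50% | 0.36 | 1.413 | 0.403 |

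Two-sided at 0.05 the powers are 0.795, 0.551 and 0.285. They should not be set beside the one-sided 5% error rates in step 3, because no single test has both.

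**The case for a change.** The best case for a change is that it is cheap and closes a real opening. The analysis plan is very short, nothing in it forbids choosing the time late, and the Synopsis and session procedures differ. Figure 1 might list several SF-MPQ times without making one primary, and the analysis text does not refer to it. One sentence naming the score would leave the 66 patients untouched, and would leave power at 0.79 if 0.72 and 2.07 hold at that time.

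Much of this stands: the time is not stated, and the two descriptions of the pain schedule need reading together. Three things weaken the step to a required change.

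- **The count of competing primary scores is inferred.** The SF-MPQ is named only in the Statistical Analysis Plan. The session text says only pain, and B.2 also uses a pain VAS. If the SF-MPQ is given once after dosing, the choice largely disappears.
- **The documents do not point to one time.** Acute effect in Aim 1 fits 10, 20 or 60 minutes. The Blood Sampling paragraph gives the early and delayed times equal standing. Blood paired with pain exists at 60 minutes as well as at 10, so the correlations in Aim 1c do not favour 10, and a 10-minute score would precede the stated 20-minute peak. A prespecified average would serve too.
- **Evidence of different analgesia by time is thin.** The taper over 2–3 hours concerns psychotropic effects, not pain.

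**Conclusion.** The concern identifies missing detail, not an error. The primary comparison as written is valid for any single post-dose score settled before treatment codes are linked to results, and settling it is an ordinary step in preparing the analysis. The stated power is correct for a score that carries the assumed 0.72 points with SD 2.07.

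The inflated error rates (6.8–8.8% for two times, 8.8–14.4% for four, one-sided 0.05) apply only if the time is picked after seeing the data, which no part of the plan proposes, and they rest on assumed correlations of 0.9 to 0.5. The power losses (0.875 to 0.674 or 0.403) rest on assumed fractions of the effect for which the documents give no basis. Which time or summary to prefer is a fair trade-off between earliness, stated peak and duration. Figure 1 may already show the SF-MPQ times. No change to the plan follows.

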- m) body mass index below 18.0 or above 33.0 kg/m² range confirmed during medical exam (as extreme BMIs can influence drug blood levels and BMIs in the obese range are considered cardiovascular risk factors)
- n) all current asthma conditions (i.e., active symptomatic asthma within the last week) or current or past history of asthma triggered by smoking or vaping
- o) current diagnosis of dementia or Parkinson's disease
- p) scores below 23 on the Folstein Mini-Mental Status Exam
- q) current diagnosis of moderate to severe traumatic brain injury
- r) current diagnosis of epilepsy
- s) individuals who are immunocompromised (i.e., post-organ transplant, those with an immune deficiency disorder such as HIV, individuals taking immunosuppressant steroids such as continuous prednisone use, and those with lupus)
- t) past kidney disease (e.g., glomerular nephritis, polycystic kidney disease) and/or presence of elevated creatinine (levels above 2.0)
- u) cardiac disease confirmed via clinically significant abnormal findings on an EKG (e.g., arrhythmia, conduction abnormalities, ischemia, or evidence of past myocardial infarction), as well as diagnoses of congestive heart failure or cardiomyopathy
- v) abnormal vital signs (heart rate will be required to be below 50 or above 110 BPM; blood pressure above 160/100 or below 90/60; blood oxygen levels below 90%)
- w) taking any medications on our List of Exclusionary Medications
- x) presence of any severe cardiovascular, renal, or hepatic disorder
- y) below 18 or above 65 years of age
- z) use of cannabis in the past 1 month before commencement of study participation and throughout the study as confirmed via urine toxicology screening
- aa)** below minimum self-reported pain level of 30/100 on a visual analog scale (VAS) pre-study enrollment via telephone and at baseline due to potential variability in pain level

B.3. RECRUITMENT METHODS

We plan to recruit RA patients primarily from the Brown University Physician outpatient clinic and the Chapman Street Outpatient Clinic of Rhode Island Hospital. Approximately 9,000 patients with various rheumatic conditions and approximately >3,000 with rheumatoid arthritis visit these clinics annually. With the facilitation of our collaborators (please see letter of support), participants will be recruited via initial contact by providers involved in the patient's care, flyers, advertisements, mailings, and referral. Potential subjects will be screened via phone.

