Primarily, we will receive referrals from our collaborators at the Brown University Physician outpatient clinic. In addition, we will use internet advertisements on social media sites and flyers at local treatment clinics. The study PI and research assistant (both having completed all required CITI certifications) will be contacted by our collaborators in the instance of referrals, and by other interested patients with rheumatic disease (rheumatoid and psoriatic arthritis). Potential participants will be screened in person at the clinic, or via telephone or online screener. Potential participants will primarily be referred by our collaborators. Patients that meet eligibility criteria, are not well-controlled on current medications, and are deemed to potentially benefit from incorporating cannabis into their treatment regimen will be enrolled in the study.

While use of cannabis to treat chronic pain associated with various conditions (e.g., inflammatory rheumatic diseases) is approved in Rhode Island and many other states, there is limited research in this area and it is not

the standard of care for such diseases. Of note, the cannabis that will be administered in the current investigation will be an adjunct to current approved treatment regimen.

At baseline session conclusion, eligible participants will be scheduled for two 5-hour experimental CB administration sessions and randomized to either placebo or medium THC/medium CBD dose for Experimental Session 1 and will receive the other dose at the following session (Experimental Session 2). The study PI will randomize participants to the dose conditions but will not run experimental sessions. In order to maintain double-blind conditions, CB will be prepared by a pre-designated staff member with DEA clearance. Participants and other study staff working directly with participants will be blind to dose. To control for expectancy effects^{18,19}, participants will be told they will vaporize CB varying in THC in the low to moderate potency range. CB appearance is identical across dose.

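### The primary t-test has no session term in a two-period crossover, so a pain shift between sessions is counted as random error; a period-adjusted analysis avoids this at almost no cost.

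*Combined protocol and SAP*

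**What the plan says.** The sample-size paragraph of the Statistical Analysis Plan (B.4) starts from the crossover design: "We calculate the necessary sample size using a 2-period, 2-treatment, crossover design, comparing cannabis to placebo". Its inputs are a within-patient effect, "we assume that participants will have a reduction in pain of 0.72 points following active cannabis compared to placebo cannabis", and a spread for the difference, "with a standard deviation of the mean difference of 2.0715". The result is "a design encompassing 66 patients will have power equal to 0.79 to detect this difference with this standard deviation", stated "At a two-sided significance level of 0.05".

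The analysis itself is one sentence: "A one-sided t-test will be conducted to compare pain level following vaporization of each dose". It names no session, period or sequence term, and does not say whether the test is paired. No other section supplies such a term.

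Two other places bear on this. B.3 randomises the order of treatment: each patient is "randomized to either placebo or medium THC/medium CBD dose for Experimental Session 1 and will receive the other dose at the following session". B.1 calls the design counter-balanced. B.2 also promises the baseline VAS pain score as a covariate in every analysis, which a plain t-test cannot hold.

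**The concern.** In a two-period crossover each patient's treatment difference also contains the difference between the two sessions, with opposite sign in the two sequences. The randomised order exists so that the analysis can separate the two. A t-test that pools the sequences does not do this, and two things can follow.

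- With equal sequences the shift cancels from the estimate but inflates its estimated standard error. Power is lost, and the true error rate drops below the nominal one.
- With unequal sequences the shift does not fully cancel, and part of it is reported as treatment effect.

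Planned power is 0.79, so there is little to give away on the primary test of the primary outcome. The single baseline VAS covariate would not help: it has one value per patient, the same for both sessions, so it cannot represent a difference between them.

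**Working it through.** **Inputs from the Statistical Analysis Plan.** Difference 0.72; N = 66; two-sided 0.05. The SD of the difference is printed as 2.0715. This is probably 2.07 followed by citation 15, and the choice changes power by less than 0.001. I use 2.07.

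**Assumed.** The session shift p = mean pain at Session 2 minus Session 1. The documents do not give it, so I use |p| = 0.5, 1.0 and 1.5. Sequences are 33/33 unless stated.

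**1. The plan's own figure.** Noncentrality = 0.72 / (2.07/√66) = 0.72 / 0.2548 = 2.826. Two-sided 0.05 power is 0.7950 for a paired t-test (65 df) and 0.7948 for the period-adjusted crossover test (64 df). The stated 0.79 is reproduced either way, so it is right when p = 0.

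**2. How the shift enters.** Let d = placebo minus active.
- Active-first patients: d has mean 0.72 + p.
- Placebo-first patients: d has mean 0.72 − p.

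At 33/33 the ±p cancels in the mean, whose true standard error stays at 0.255. The pooled SD, however, becomes about √(2.07² + p²):
- p = 0.5: √(4.285 + 0.25) = 2.13, reported standard error 0.262
- p = 1.0: √(4.285 + 1.00) = 2.30, reported standard error 0.283
- p = 1.5: √(4.285 + 2.25) = 2.56, reported standard error 0.315

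**3. Consequence at 33/33** (unadjusted paired t-test, by simulation with 200,000 trials per setting):

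| \|p\| | Power, two-sided 0.05 | Error, two-sided 0.05 | Power, one-sided 0.05 |
|---|---|---|---|
| 0 | 0.795 | 0.050 | 0.875 |
| 0.5 | 0.78 | 0.044 | 0.865 |
| 1.0 | 0.73 | 0.030 | 0.834 |
| 1.5 | 0.64 | 0.015 | 0.775 |

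The period-adjusted test gives about 0.795 (two-sided) and 0.875 (one-sided), with error about 0.05, in every row. Both sidedness columns are shown because the sample size is two-sided, while the test is one-sided with no alpha stated.

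**4. Unequal sequences.** The unadjusted estimate moves by p × (active-first − placebo-first)/66.
- 36 active-first, 30 placebo-first: p × 6/66, which is 0.045 at p = 0.5 and 0.091 at p = 1.0.
- 40 active-first, 26 placebo-first: p × 14/66, which is 0.106 and 0.212.

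Reversing the split, or the sign of p, reverses the sign. The adjusted estimate stays at 0.72 in all these cases.

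**5. Price of adjusting when p = 0.** At 33/33 power goes from 0.7950 to 0.7948. At 36/30 it is about 0.79, and at 40/26 about 0.775.

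**The case against.** The strongest reply is that nothing shows a session shift exists, and that the design already guards against one. Much of this stands.

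- **Size.** The documents give no p. Shifts of 1.0 and 1.5 are 1.4 and 2.1 times the assumed treatment effect (1.0/0.72 and 1.5/0.72). At 0.5 the loss is about 2 points of power.
- **Regression to the mean.** A reader might infer a downward drift from the entry rule, which excludes patients "below minimum self-reported pain level of 30/100 on a visual analog scale (VAS) pre-study enrollment via telephone and at baseline". That rule does not support the inference. Both treatment sessions come after the selection, so regression to the mean would by itself lower them about equally. B.4 also has pain level reconfirmed on the morning of each session and fixes the vaporization start time to limit variation in pain. First exposure to the study procedure at Session 1 remains a possible cause of a shift, but an unquantified one.
- **Bias.** A reader might infer that the planned test is biased or inflates false positives. With balanced sequences, which B.1 intends, it does neither. Averaged over simple random assignment the estimate is also unbiased. The shift in step 4 is conditional on the realised split and can go either way.
- **One-sided power.** If the test is run at one-sided 0.05, power stays above 0.79 until the shift is well above 1.0.
- **Pairing.** A reader might take the sentence to mean an unpaired test. Sizing on the SD of a difference points to a within-patient comparison. The missing word should be added, but the plan does not commit to an unpaired test.

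A period-adjusted crossover t-test may even have been intended. The text does not say so. None of these replies gives a reason to prefer the unadjusted test.

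**Conclusion.** The point holds as a should-fix: a free improvement to the primary analysis. As written, the t-test ignores the session and sequence structure on which the trial was randomised and sized.

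For |p| between 0.5 and 1.5 with 33/33 sequences, the cost is about 2 to 16 points of two-sided power (0.795 down to 0.78 and 0.64), or 1 to 10 points at one-sided 0.05 (0.875 down to 0.865 and 0.775). The test is conservative in both cases. Bias arises only if the analysed sequences are unequal. No allocation method, dropout rate or plan for lost second sessions is given, so that cannot be excluded, but neither is it predicted.

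These figures rest on the plan's 0.72, an SD read as 2.07, all 66 patients analysed, and an assumed shift. The plan's 0.79 is correct if there is no shift.

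**What to change.** Replace the t-test sentence with a named crossover analysis, for example:

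> The primary analysis estimates the active-minus-placebo difference in SF-MPQ pain from a linear mixed model with treatment, session and sequence as fixed effects, baseline VAS pain as a covariate and patient as a random effect, reported with a 95% confidence interval.

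An equivalent core is a comparison of the within-patient session differences between the two randomised sequences, where half the between-sequence difference estimates the treatment effect. Baseline VAS can be added there as a covariate. In a model with fixed patient effects it would drop out, because it is constant within a patient. One of the other two forms is therefore needed to honour the statement in B.2.

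Use the same model for negative affect and the inflammatory markers. State the sidedness and alpha in the same place, so that the test matches the sample-size paragraph.

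Cost: SAP wording and one degree of freedom for session (power 0.7950 to 0.7948 with no shift and equal sequences). The baseline covariate takes one more, but B.2 already commits to it. No extra patients, visits or data are needed.
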